**Subjective safety and tolerability measures:**

**Treatment adherence.** Compliance will be measured by pill counts performed every 3 months. The number of pills taken out of the total prescribed in a 3-month period will be modeled as a random effects binomial regression model [105]. The binomial rates from 8 time points (month 3 to 24) will be modeled as unstructured mean model with 7 indicator variables as well as polynomial models over time. The random-intercept and the random intercept and slope models will be considered. The significance of the time indicators or parameters by treatment interaction will be evaluated for treatment difference in compliance.

Voluntary withdrawals will be examined at the end of the study by comparing the percent of withdrawals between the treatment groups using a chi-square test or Fisher's exact test.

**Patient reported symptoms.** The outcomes will be scored as a 5-point Likert-type scale (0 to 4) in response to questions on how much the patients are bothered by certain symptoms. The questionnaire will be administered every six months, for a total of five time points. The responses will be treated as normally distributed, as ordinal or dichotomized variable, and we will apply the linear mixed effects model or GLMM methods to compare changes between treatment groups. Because of additional time points available, in addition to the unstructured mean model, we will also fit piecewise models with join point at 6 months, considering linear and curvilinear trajectories between 6m and 24m time points.

***Exploratory Aim 1: To examine the modifying effects of demographic, clinical, and molecular characteristics on both efficacy and safety markers.***

As the primary aim of this trial is to examine the main effects of low dose tamoxifen treatment on MBD, we will examine the modifying effects of demographic, clinical, and molecular characteristics as exploratory analysis. Even if time by treatment interaction (main treatment effect) is not significant, examining the modifying effects of covariates may reveal subgroups that respond differently to low dose tamoxifen. A three-way interaction of time by treatment by modifying variable will be included in the longitudinal model containing a two-way time by treatment group interaction. Modifying effects will be considered statistically significant if the three-way interaction is significant. The covariates of interest are described below.

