### 3.7 **Administration**

Trial participants will be instructed to take one capsule per day orally. They will be instructed to swallow the capsule whole, with water or another non-alcoholic liquid, preferably the same time each day. They may take the capsules with or without food. If they forget a dose, participants will be asked to take it when they remember, and then take the next dose as usual, but if they do not remember until their next dose, to not take extra capsules to make up the missed dose.

For premenopausal subjects, they will be instructed to begin their study medication course while menstruating or after negative beta-HCG test as below. For premenopausal subjects who do not have regular menstrual periods or are between periods, a beta-HCG level will be performed to confirm that the patient is not pregnant before starting study medication. Participants will be warned that they should avoid pregnancy while taking study medication and for two months after discontinuation. They will be advised to use barrier or nonhormonal contraceptive measures.

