**Adverse events:** We assume the rate of grade 2-4 toxicities in the placebo group to be low, at 0.5%. At the end of the study, with 94 women in each arm (accounting for 10% attrition per year), the study will have at least 80% power to detect an adverse event rate of 9.1% in the low dose tamoxifen group based on Fisher’s exact test and Type I error=0.05.

**Adherence to therapy:** We will examine the difference in adherence rates of the treatment groups by comparing the percent of pills taken across 8 time points. With 115 women at baseline per arm, assuming a constant adherence rate of 90% in the placebo group and a between-measurement correlation of 0.6 and 2-sided alternative, there will be 80% power to detect an adherence rate of about 77% in the low dose tamoxifen group.

**Voluntary withdrawals:** If the proportion of patients in the placebo arm who withdraws voluntarily by the end of the study is 10%, then with 115 women in each arm at baseline, assuming type I error=0.05, the study will have 80% power to detect a significant difference in the voluntary withdrawal rate in the low dose tamoxifen group if the withdrawal rate in the intervention group is about 28%.

**Safety biomarkers:** We focus here on total cholesterol (TC), anti-thrombin-III (AT-III), bone-specific alkaline phosphatase (BSAP), and urine N-telopeptide crosslinks (NTX). With the proposed sample sizes, the detectable effect size (described earlier) is 0.34. A relatively small % change in mean levels is detectable for TC and AT-III but larger % changes are needed to detect a significant treatment difference at t2 for BSAP and NTX.

Outcome	Assumed levels at t0 for Placebo and Low dose Tamoxifen groups	Detectable levels at t2 (80% power) for Low dose Tamoxifen group	
	Mean ± SD	Mean	Relative % change (from t0)

TC* (mg/dL)	199 ± 45	214.3	8% ↑
AT-III** (%)	100 ± 13.3	95.5	5% ↓
BSAP  (µg/L)	7.7 ± 4.5	6.2	20% ↓
NTX  (nM BCE/mM)	24.4 ± 16.1	18.9	23% ↓

\* Mean obtained from [111], sd obtained from [112]

\*\* per ARUP reference laboratory

Thus, we expect to be able to detect a 5-23% difference in the objective safety biomarkers proposed as secondary endpoints.

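### The adherence model has no term for a woman's period-to-period swings, so its unstructured arm-by-time test can reject far too often if pill-taking varies beyond binomial noise

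*Combined protocol and SAP*

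**What the plan says.** Section 12.4, under subjective safety and tolerability measures, sets the data source: "Compliance will be measured by pill counts performed every 3 months". The model is then given: "The number of pills taken out of the total prescribed in a 3-month period will be modeled as a random effects binomial regression model". On the mean structure: "The binomial rates from 8 time points (month 3 to 24) will be modeled as unstructured mean model with 7 indicator variables", with polynomials in time as an alternative. On the random effects: "The random-intercept and the random intercept and slope models will be considered". On the test: "The significance of the time indicators or parameters by treatment interaction will be evaluated for treatment difference in compliance".

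Section 12.4 assigns non-normal longitudinal data to Proc GLIMMIX. For the adherence model it names no woman-by-period effect, beta-binomial variance, scale parameter or robust standard error, and it does not say which combination of mean model and random effects governs.

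Section 12.5 powers this endpoint on 115 women in each arm at entry, with placebo adherence fixed at 90% over time. For the repeated counts it takes "a between-measurement correlation of 0.6 and 2-sided alternative". It reports 80% power against about 77% on tamoxifen.

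Sections 6.3 and 14.3 end treatment only when an interruption exceeds 90 consecutive days. Shorter interruptions can occur in women who stay on study.

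**The concern.** The arm-by-time terms compare how adherence changes from period to period within women in the two arms. Their standard errors therefore depend on within-woman, between-period variance. A random intercept absorbs a woman's overall level, and a random slope absorbs a steady drift. Neither absorbs a bad quarter followed by recovery, which is what a hold of a few weeks produces. Whatever the random effects miss, the model counts as binomial noise from about 90 pills. If the true variation is larger, the standard errors are too small.

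Adherence is a named tolerability measure under Aim 2. An arm difference declared on noise would misstate how well the 5 mg regimen is tolerated.

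**Working it through.** **Inputs from the documents.** Section 3.7: "Trial participants will be instructed to take one capsule per day orally", so about 90 pills per 3-month period. Section 12.5: 115 women per arm, 90% placebo adherence, correlation 0.6 between periods, two-sided; 94 per arm remain after 10% yearly attrition (stated for adverse events). Section 12.4: 8 periods, hence a 7-df unstructured interaction test. Alpha 0.05 is stated for neighbouring endpoints and taken to apply here.

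**Assumed, because the documents do not give it.** The total SD of a woman's period adherence rate.

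**Step 1: the plan's own power figure.** For 90% versus 77%, 80% power and two-sided 0.05, the two-proportion formula gives 127 per arm, or 142 with a continuity correction. Averaging 8 equally correlated measurements multiplies this by (1 + 7 × 0.6)/8 = 0.65. With the correction, 142 × 0.65 = 92.3 completers (plan: 94), and 92.3/0.81 = 114 at baseline (plan: 115). Without it, 127 × 0.65 = 83 completers and 102 at baseline. So the figure reproduces with a continuity correction that the plan does not name, and with each woman-period given the variance of a single yes/no outcome, p(1−p).

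**Step 2: what the analysis model allows.** At 90% adherence the binomial variance of a period rate is 0.9 × 0.1/90 = 0.001, an SD of 3.2 points.

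**Step 3: approximate size.** With correlation 0.6, 40% of the period-rate variance lies within women. The ratio of actual to modelled within-woman variance is k = 0.4 × SD²/0.001. Standard errors are too small by √k, and the approximate 7-df error is P(χ²₇ > 14.07/k).

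| Assumed total SD | k | √k | Approximate 7-df error |
|---|---|---|---|
| 5 points | 1.00 | 1.0 | 5% |
| 6 points | 1.44 | 1.2 | 20% |
| 8 points | 2.56 | 1.6 | 60% |
| 10 points | 4.00 | 2.0 | 83% |

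**Step 4: simulation under no arm difference.** 115 per arm, 8 periods, 90 pills, 90% mean adherence, correlation 0.6, no attrition. Data came from a logit-normal model with woman and woman-by-period effects. Binomial mixed models were fitted by penalised quasi-likelihood with Wald tests, 200 trials per setting (Monte Carlo standard error about 1.5 points near 5%). The first row is the ratio of the empirical to the model standard error for the last-period interaction; the others are false-positive rates.

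| | SD 5 | SD 6 | SD 8 | SD 10 |
|---|---|---|---|---|
| Standard-error ratio | 1.08 | 1.17 | 1.52 | 2.10 |
| 7-df, random intercept | 4% | 16% | 62% | 92% |
| 7-df, intercept and slope | 3% | 15% | 57% | 87% |
| Linear, random intercept | 7% | 8% | 23.5% | 35.5% |
| Linear, intercept and slope | 4.5% | 5.5% | 3.5% | 5% |

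The linear test with intercept and slope stayed between 3% and 5.5% up to an SD of 20 points. Polynomials above linear were not simulated.

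**Step 5: is such variation plausible here?** Two separate null simulations placed holds directly into otherwise binomial data. With none, the 7-df test rejected about 5% to 6% of the time. With an assumed 30-day hold in 1% of woman-periods it rejected about 38% to 40%. The hold frequency is an assumption.

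**The case against.** The strongest reply is that the plan already handles clustering. Pills are independent only conditional on the woman's random effects, so a reader who infers that the model treats all pills as independent goes beyond the text. That stands.

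Second, not every planned version fails. The linear-in-time test with random intercept and slope keeps its error rate. That also stands, but the plan does not make that version the governing one.

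Third, the size rests on an SD that the documents do not give. At a total SD of 5 points with correlation 0.6 there is no inflation, so the documents do not support saying that false positives are likely in this trial. The interruption argument is conditional too: the plan does not say whether held days count as prescribed pills. If they were removed from the denominator, that source would shrink.

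Fourth, a reader might set the power calculation's within-woman variance, 0.4 × 0.09 = 0.036, against the model's 0.001 and conclude that the true variance is 36 times too large for the model. It does not follow. The ratio is 0.4 × 90 by construction. The 0.036 is inferred backwards from the power figure, and p(1−p) is the largest variance a rate with mean p can have. Sections 12.4 and 12.5 also address different contrasts: arm-by-time interaction and a constant difference. The comparison shows only that the power figure appears to assume a much larger per-period variance than the analysis model allows.

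Finally, no success or stopping rule rests on this test, and the primary density analysis does not use this model.

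**Conclusion.** The point holds for the unstructured 7-df test under either planned random-effects structure, and for the linear test with a random intercept only. As specified, these leave period-specific variation out of the standard errors. Under the simulation's assumptions the 7-df error is near nominal at a total period-rate SD of 5 points, about 15% to 16% at 6 points, and 87% to 92% at 10 points. The threshold is low because binomial noise from 90 pills is small. Which of these values applies cannot be known from the documents. The consequence is confined to a secondary tolerability conclusion, but the planned test could give a wrong answer there, and the repair is cheap enough to make in advance.

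**What to change.** State in Section 12.4 that the binomial adherence model will include a woman-by-period random effect. In the simulation this gave a 7-df error of 2%, 6.5%, 5.5% and 7.5% at SDs of 5, 6, 8 and 10 points, and 3.5% and 5% at 15 and 20. The data were generated with such an effect, so this is a favourable test of it.

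Give woman-clustered robust standard errors as a sensitivity analysis. On the random-intercept model they gave 4% to 10.5% for the 7-df test, a large improvement but not exact. Do not rely on a single Pearson scale factor: its error rose from 3% at an SD of 5 points to 16.5% at 10 and 43.5% at 20.

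Name the mean model and random-effects structure that govern the conclusion, and say how held days enter the number prescribed. In Section 12.5, state the per-period variance and align it with the amended model.

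The cost is one extra model term, a few sentences, and wider intervals for the arm-by-time terms.

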## 12.5 Power and sample size:

***Aim 1:*** *To determine the impact of low-dose tamoxifen on surrogate endpoint biomarkers of BC risk.*

**Mammographic breast density (MBD):** The primary efficacy endpoint of the trial is MBD. The efficacy of low dose tamoxifen will be examined by comparing the slopes in the longitudinal linear regression of the MBD on time since treatment initiation between the low dose tamoxifen group and placebo control group. For sample size calculation, we let Y, the response, as the mean of the square root of MBD (RTMBD) from both breasts. Because of randomization, we expect no difference between the expected values of Y at t0 between treatments but expect the linear slopes of the two groups to diverge over time, if the intervention is efficacious. Power/sample size calculation was conducted by assuming a linear change in RTMBD over time and various magnitudes of RTMBD difference expected at t2 between the treatment and control groups.

Longitudinal power calculation requires specification of the expected linear trend (thus the expected values of Y at t0, t1, t2) for the controls, the variance/covariance of the repeated measurements, the expected difference in Y at t2 between the treatment groups, and the correlations among repeated measurements. These estimates were obtained from 41 control women in the Puget Sound NSABP P-1 participating sites, [106] 16 pre-menopausal women (median age=50, range=38-50) and 25 post-menopausal women, (median age=57, range=36-74), with data on MBD expressed as a percent breast density at pre-, 1-yr, and 2-yr post-treatment. Although this entire control sample (median age=50, range=36-74) is older than the available CPIR HL cohort (median age=35, range 25-50), based on changes in MBD observed with hormonal fluctuations during the menstrual cycle [66] and after discontinuation of exogenous hormone in postmenopausal women [70], it can be reasonably assumed that estrogen withdrawal associated with menopause has a greater impact on variation in MBD than age alone. Thus, we assumed that the estimates obtained from these women can be applied to the anticipated CAYAC patient control sample.

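### The only named test of adherence is the time-by-treatment interaction, which cannot detect a steady gap in pill-taking between the arms

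*Combined protocol and SAP*

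**What the plan says.** Section 12.4, Aim 2, Treatment adherence, takes pill counts every three months as binomial counts in a random-effects model. "The binomial rates from 8 time points (month 3 to 24) will be modeled as unstructured mean model with 7 indicator variables", with polynomial time models as an alternative. The test is then named: "The significance of the time indicators or parameters by treatment interaction will be evaluated for treatment difference in compliance". Neither the treatment main effect nor mean adherence over the study is named as a test.

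Section 12.5, Aim 2, Adherence to therapy, describes the comparison as "comparing the percent of pills taken across 8 time points". Its inputs are "With 115 women at baseline per arm" and "assuming a constant adherence rate of 90% in the placebo group and a between-measurement correlation of 0.6 and 2-sided alternative", and it concludes that "there will be 80% power to detect an adherence rate of about 77% in the low dose tamoxifen group". It does not say whether 77% is a constant rate, an average, or the rate reached at month 24. It also does not say which test was powered.

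For mammographic density, Section 12.5 gives the reason an interaction test works: "Because of randomization, we expect no difference between the expected values of Y at t0 between treatments".

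**The concern.** For density, randomization makes the arms equal at t0, before any drug is taken. Any treatment effect must then appear as a departure from that common start, and the time-by-treatment interaction measures exactly this. Adherence has no t0. With eight on-treatment periods and seven indicators, the reference period is itself on treatment. The interaction terms measure only how the gap changes from its value in that period. A gap already there at month 3 that does not change makes every interaction term zero, on the rate scale and on the logit scale.

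An early, lasting gap is not far-fetched. Section 2.2 says that symptoms at 20 mg can interfere with compliance. Section 3.4 puts steady state at about 4 weeks for tamoxifen and about 8 weeks for its main metabolite, both before the first three-month count. Whether this carries over to 5 mg is an inference; the protocol expects better tolerability at that dose.

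Tolerability is objective 1.2. The risk is that a non-significant interaction is reported as no difference in compliance when women on tamoxifen took fewer pills throughout.

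**Working it through.** **Inputs.** From Section 12.5: placebo 90% in every period, tamoxifen 77%, correlation 0.6 between periods, two-sided test, 115 per arm at baseline. Assumed: alpha 0.05 and 94 per arm after 10% attrition per year (both stated in the adverse-event paragraph of 12.5 but not repeated for adherence); variance p(1−p) per period; equal correlation between all pairs of periods.

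**1. Can the stated 77% be reproduced?** Yes, in two different ways.

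(a) *Steady gap, test of the average.* The mean of eight equally correlated values has variance factor (1 + 7 × 0.6)/8 = 0.65. For 0.90 versus 0.77 at 80% power, a single two-proportion comparison needs

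n = [1.96 √(2 × 0.835 × 0.165) + 0.842 √(0.09 + 0.1771)]² / 0.13² = 126.8 per arm.

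With continuity correction, n/4 × [1 + √(1 + 4/(0.13n))]² = 141.8. Then 141.8 × 0.65 = 92.1, rounded up to 93, and 93/0.81 = 114.8, or 115.

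(b) *Equal at month 3, linear divergence to 77% at month 24, 7-df interaction.* Power is 79% with 94 per arm. The detectable month-24 rate is 76.9%.

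The stated figure therefore does not reveal which pattern or test was assumed.

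**2. Power of the interaction for a steady gap.** The seven contrasts compare the gap in each later period with the gap at month 3: each is 0.13 − 0.13 = 0. The noncentrality is 0 whatever n is, so power equals alpha, 5%. The linear interaction gives the same result.

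**3. Power of the averaged effect for the same gap.** SE = √[(0.09 + 0.1771) × 0.65/n].

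- n = 115: SE = 0.0389, z = 0.13/0.0389 = 3.35, power = Φ(3.35 − 1.96) = 92%.
- n = 94: SE = 0.0430, z = 0.13/0.0430 = 3.02, power = Φ(3.02 − 1.96) = 86%.

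**4. Other patterns.** With Σ the covariance of the eight between-arm differences and C the contrast matrix, noncentrality is (Cd)ᵀ(CΣCᵀ)⁻¹(Cd), referred to a noncentral chi-square. Power is shown for 115 / 94 per arm:

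| Tamoxifen course | 7-df interaction | Averaged effect, 1 df | Joint 8-df test |
|---|---|---|---|
| 77% throughout | 5% / 5% | 92% / 86% | 65% / 54% |
| Half the gap at month 3 (83.5%), then 77% | 28% / 23% | 89% / 82% | 74% / 63% |
| 90% at month 3, linear to 77% at month 24 | 88% / 79% | 45% / 38% | 88% / 79% |

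In the last row the mean rate on tamoxifen is 83.5%, so the average gap is only 6.5 points. That is why the averaged effect does poorly there.

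**5. Simulation check.** In 10,000 trials of correlated binary data with a steady 90% versus 77%, rejection rates at 115 / 94 per arm were 4.6% / 4.7% (7-df interaction), 4.8% / 5.3% (linear interaction) and 91.3% / 86.0% (average).

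**The case against.** Five points can be made for the plan.

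- *Section 12.5 can be read as intending a comparison of levels.* It can, but it names no test, and Section 12.4 names a different one. That reading makes the mismatch sharper.
- *The 5% figure assumes a separate treatment main effect in the adherence model, which 12.4 does not spell out.* This is true. If the model forced a common month-3 value, a steady gap would leak into the interaction terms, and 7-df power would be about 25% (115 per arm) or 20% (94). That is still far below 80%, and it would impose equality at a time when nothing guarantees it.
- *An exactly constant gap is an extreme case, and p(1−p) may overstate the variance, since each period is a count of many pills.* This stands in part. With half that variance, the half-gap pattern gives 46% to 56% interaction power; with a quarter, 81% to 90%. The steady case stays at 5% whatever the variance.
- *The averaged effect is not best for every pattern.* This is correct, as the third row of the table shows. A joint 8-df test covers both patterns, but it gives up much of the power against a steady gap (54% to 65%).
- *The analysis is secondary.* This also stands. Withdrawals, symptoms and toxicities have their own comparisons between the arms, and adherence by period would still be estimated. None of these tests pill-taking between arms. The as-treated density analysis in 12.4 sets placebo adherence to 0, so it cannot do so either.

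**Conclusion.** The concern holds. As written, the named test of compliance would be non-significant about 95% of the time, at any sample size, when tamoxifen adherence is lower by a constant amount from month 3 onward. A test of the averaged effect would detect 90% versus 77% with 86% to 92% power. The steady-gap result for the interaction depends only on the model having its own treatment main effect. The other power figures also rest on the stated correlation of 0.6, alpha 0.05 and binomial variance per period.

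The claim of 80% power at about 77% is not shown to be wrong. It can be reached under a steady gap with a test of the average, or under a widening gap with the 7-df interaction. A constant 90% set beside a single 77% reads most naturally as a steady gap, and for that the test in 12.4 has 5% power, not 80%. This should be corrected, but it concerns one secondary analysis; the primary endpoint and the accrual target do not change.

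**What to change.** In Section 12.4, name the treatment effect averaged over the eight periods (1 df, from the same binomial mixed model) as the test of a difference in compliance. Keep the time-by-treatment interaction as a secondary test of whether the gap changes over time, since it is the stronger test when the arms diverge.

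In Section 12.5, state that the power refers to this averaged difference with a constant rate in each arm. The figure of about 77% can stay as a conservative one, because the averaged test has 86% to 92% power at that rate.

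The cost is one sentence and one clause. No extra data or patients are needed.

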Participants must not be planning to become pregnant for two years to be eligible for the study, and they will be warned about the importance of not becoming pregnant while on study at the time of enrollment. They will be advised to use either a barrier method or another nonhormonal form of contraception (eg. hormone-free IUD) for all sexual activity during the course of the study. Nevertheless, occurrence of an unplanned intrauterine pregnancy while on study will be an indication for immediately stopping treatment and the patient must withdraw from the study. If the patient should become pregnant while on study, or within two months after discontinuing therapy, her treatment assignment will be unblinded immediately. If the patient was randomized to tamoxifen, then they must be apprised of the potential risk of spontaneous abortion, birth defects, or a DES-like syndrome.

The Principal Investigator (PI) at each site is responsible for monitoring protocol conduct and reporting to their Institutional Review Board (IRB) any adverse events (AEs) related to either the study medication per their institutional guidelines. AEs must also be reported to the Coordinating Center (UAB) per instructions in Section 8.0. The NCI common toxicity criteria for adverse events Version 4.0 (CTCAE v.4.0, Publish Date 10/19/2009) will be used to assess toxicity.

With the exception of vasomotor and gynecologic symptoms commonly associated with menopause, all grade 2 or greater toxicities of clinical significance with *possible* or greater attribution (please refer to Section 8.3 for definition) to the study drug will be reviewed by the Protocol Management Team (PMT) at the local site. The PMT includes the consortium PI, the consortium co-investigator, and the CRA/CRN.

- Any grade 2 toxicity besides vasomotor and/or gynecologic symptoms commonly associated with menopause with *probable* or greater attribution to the study drug will be brought to the attention of the local PI (within 24 hours of knowledge of the event) for close monitoring. If the symptom resolves or improves within 72 hours, the patient may continue on the study medication. Otherwise, the patient will be unblinded and taken off therapy.
- A patient reporting grade 3-4 toxicity with *possible* or greater attribution to the study drug will be unblinded and taken off protocol therapy.

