#### Study End Form:

The CRA/CRN will fill out the **Study End Form** at the time the subject goes off trial, even if they complete the full treatment course. This form records whether or not the subject completed the trial per protocol, voluntarily withdrew, or was withdrawn for another reason. For voluntary withdrawals, subjects will be asked to clarify if it was due to intolerable side effects of treatment or if it was due to another reason.

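### The only planned withdrawal comparison counts voluntary withdrawals, so women taken off drug under the toxicity rules are scored as non-withdrawals

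*Combined protocol and SAP*

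**What the plan says.** Aim 2 is to establish safety and tolerability. Under its subjective measures, section 12.4 plans two analyses of persistence with study drug.

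- **Withdrawal:** "Voluntary withdrawals will be examined at the end of the study by comparing the percent of withdrawals between the treatment groups". Fisher's exact test is offered as the alternative to chi-square.
- **Adherence:** "The number of pills taken out of the total prescribed in a 3-month period" is the outcome of a random-effects binomial model over eight 3-month periods. The section does not say how periods after a permanent stop are scored.

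Section 12.5 powers the withdrawal comparison on voluntary withdrawal alone. With 10% assumed on placebo, about 28% detectable on tamoxifen, alpha 0.05 and 115 women per arm, it states that "the study will have 80% power to detect a significant difference in the voluntary withdrawal rate in the low dose tamoxifen group".

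Stopping is not always the woman's choice.

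- The opening list in section 6.3 ends treatment for a grade 2 toxicity of probable or greater attribution that has not resolved within 72 hours, and for grade 3 or 4 toxicity of possible or greater attribution.
- Later in 6.3, a grade 2 toxicity that resolves or improves within 72 hours allows treatment to continue. "Otherwise, the patient will be unblinded and taken off therapy". That text exempts menopausal-type vasomotor and gynecologic symptoms.
- 6.3 also lists DVT, PE, TIA, CVA, retinal vein thrombosis and cardiac ischemia or infarction as indications to stop.
- Section 7.3.1 stops treatment for an adverse event that the investigator considers drug-related or likely to interfere with compliance. It sets no grade and points back to 6.3.

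The Study End Form separates women who completed from those who "voluntarily withdrew, or was withdrawn for another reason". Only voluntary withdrawals are asked whether side effects were the reason.

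**The concern.** A woman removed under a toxicity rule is a clear case of treatment that could not be continued, yet the withdrawal comparison scores her as not having withdrawn. Removal also takes her out of the group that could still withdraw voluntarily. More mandated stops in an arm therefore lower that arm's voluntary percentage, so the measure moves in the wrong direction as drug-related removals rise. No comparison of stopping for any reason, or of stopping for toxicity, is planned alongside it.

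The adherence model may share the problem. If nothing is prescribed after a stop, later periods have no denominator and would probably drop out. The fitted rate would then describe women still on drug. At stake is whether the reported persistence results can be read as evidence of tolerability.

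**Working it through.** **1. The plan's own figure.** Inputs from 12.5: 115 per arm, 10% v 28%, alpha 0.05 (taken as two-sided). Normal approximation with pooled null variance:

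z = [|p2 − p1|·√n − 1.96·√(2·p̄·(1 − p̄))] / √(p1(1 − p1) + p2(1 − p2))

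With p̄ = 0.19: (0.18 × 10.724 − 1.96 × 0.5548) / 0.540 = (1.930 − 1.087) / 0.540 = 1.56, so power is 94%. Exact Fisher power is 93%. The rate detectable at 80% power is about 24% (normal) to 25% (Fisher). The stated 28% does not reproduce. It is conservative and is a separate matter from this point.

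**2. Voluntary v any-cause stopping.** The documents give no rate of toxicity removal, so the rate m is assumed. Assume also that 10% of women not removed withdraw voluntarily in each arm. This borrows the plan's placebo rate and applies it to both arms.

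Voluntary = 0.10 × (1 − m). Any reason = m + voluntary.

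For m = 2% v 15%: voluntary is 0.10 × 0.98 = 9.8% v 0.10 × 0.85 = 8.5%; any reason is 2 + 9.8 = 11.8% v 15 + 8.5 = 23.5%.

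The chance of significance is by exact enumeration of the two-sided pooled chi-square test, 115 per arm:

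| Removal m, placebo v tamoxifen | Voluntary | Chance of p<0.05 | Any reason | Power |
|---|---|---|---|---|
| 2% v 15% | 9.8% v 8.5% | 7% | 11.8% v 23.5% | 65% |
| 2% v 20% | 9.8% v 8.0% | 8% | 11.8% v 28.0% | 88% |
| 0.5% v 9.1% | 9.95% v 9.1% | 6% | 10.5% v 18.2% | 39% |

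The last row borrows the grade 2-4 toxicity rates in 12.5 as removal rates.

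**3. The plan's own gap, split by route.** Read 10% v 28% as stopping for any reason and move part of the 18-point excess to rule-based removal:

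- None moved: voluntary 28%, power 94%.
- Half moved: 10 + 9 = 19%, power 49%.
- All moved: 10%, and the test has no more than its false-positive rate.

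**4. Would the planned toxicity test see these women?** Apply the two-sided Fisher test in 12.4 to the removed women alone, 115 per arm. Power is 95% (2% v 15%), over 99% (2% v 20%) and 87% (0.5% v 9.1%). Graded events that do not end treatment could dilute this.

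**5. Adherence.** Assume 90% of pills taken while on drug and 18% of women removed evenly over 24 months. If later periods drop out, the rate stays at 90%. With later periods scored as zero, the average is 0.90 × (1 − 0.18 × 0.5) = 82%, and at month 24 it is 0.90 × (1 − 0.18) = 74%.

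**The case against.** A reader might infer that a poorly tolerated drug could pass the whole of Aim 2 as if it were placebo. The documents do not support that. Section 12.4 compares grade 2-4 toxicities by arm with Fisher's exact test and models patient-reported symptoms. Its second exploratory aim compares thromboembolic events and gynecologic symptoms. Section 10.0 reports toxicity status for all eligible women and accounts for all who begin treatment in the patient-reported summaries. Step 4 shows that the toxicity test could be more sensitive to these women than a comparison of stopping for any reason. This stands. What remains is that the toxicity table counts events, not stops. It does not separate a grade 2 event that settled with drug continued from one that ended treatment.

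A reader might also infer that removed women are absent from the adherence analysis. They contribute until they stop. After that the plan is silent, so their dropping out is a likely reading and not a stated rule.

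Three further points stand. The removal rates are assumed, and the 15-20% used for tamoxifen exceeds the plan's 9.1% for grade 2-4 toxicity. The voluntary gap in favor of tamoxifen is under two points, in effect a null result. Under the exemption in 6.3, many women leaving for grade 2 vasomotor or gynecologic symptoms would be voluntary withdrawals and would be counted.

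Finally, stopping for any reason is not a clean tolerability measure. Section 6.3 also stops drug for breast events, pregnancy and death. If tamoxifen works, breast events would be commoner on placebo and would offset intolerance on tamoxifen.

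**Conclusion.** The point holds for the withdrawal measure. As defined, it omits the stops most clearly caused by the drug and falls slightly in the arm that has more of them. That follows from the text alone. The size depends on removal rates that the documents do not give: under the assumed 2% v 15%, a difference of 11.7 points in stopping for any reason (11.8% v 23.5%) appears as 1.3 points the other way. For adherence the finding is narrower: scoring after a stop is unspecified, and the denominator makes an on-drug rate the likely result. The toxicity, symptom and thromboembolic comparisons would still show much of any harm, so the defect does not extend to the tolerability assessment as a whole. The correction is worth making because it is specific and cheap.

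**What to change.** **In 12.4, Aim 2:**

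- Compare premature permanent discontinuation of study drug by arm among all randomized women, as a proportion and as time to discontinuation.
- Show (a) stops for toxicity or intolerance, meaning rule-mandated removals plus voluntary withdrawals attributed to side effects on the Study End Form, as the tolerability measure; and (b) stops for any reason, with breast events, pregnancy and death shown separately. Keep voluntary withdrawals as a component.
- State that the pills-prescribed model describes adherence while on drug. Add a sensitivity version with planned days as the denominator and zero pills after permanent discontinuation.

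**In 6.3 and 7.3:** the opening list in 6.3, the later text in 6.3 and section 7.3.1 differ on which toxicities require removal. They must be reconciled so that stops are coded the same way at every site.

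**Cost:** SAP wording, one table and one curve. The Study End Form already separates the main categories. The protocol does not say that the form subdivides its other-reason category, so the cause of those stops may have to be taken from the adverse event, breast event and treatment withholding forms already in use.
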